8.2.3 Statistical methods

8.2.3.1 Overall Survival

In the ITT:

OS will be compared between arm 1 versus arm 3 and/or arm 2 versus arm 3 when 170 deaths (118 per comparison) are observed.

Differences between the treatment groups in OS will be assessed by a Logrank test stratified by the randomization stratification factors, testing the null hypotheses (H1: Arm 1 is not superior to Arm 3 in OS; H2: Arm 2 is not superior to Arm 3 in OS, respectively). The hazard ratios of the two treatment arms over the control arm will be calculated by Cox's proportional hazards model (score test) stratified by randomization stratification factors.

The OS probability at 12 months (OS12), at 2 years (OS24) and the median OS (mOS) will be estimated from the Kaplan-Meier OS curve. Two-sided 95% CI will be computed based on the Greenwood's formula. For the median the Reflected Method will provide two-sided 95% CI.

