8.2.3.4 OS and PFS in patients with EGFRvIII mutation

In the ITT (for PFS, RANO criteria assessed by IRC):

OS and PFS analyses will be performed in the subgroup of patients with EGFRvIII mutation at final analysis. The same methodology as for analyses in the whole cohort will be applied (see sections [8.2.3.1](#), [8.2.3.2](#)).

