Close Observation

It is appropriate to initiate close observation to determine whether the abnormalities are improving or worsening and to consider whether the subject meets criteria for stopping study drug if symptoms suggestive of liver injury (as described above) persist or if repeat testing shows:

- ALT or AST > 5x ULN (or 5x baseline if elevated or >8x ULN, whichever is lower) or
- ALT/AST > 3x ULN **and** total bilirubin > 2x ULN.

It is critical to initiate this close observation immediately upon detection and confirmation of early signals of possible DILI, and not to wait until the next scheduled visit or monitoring interval. The primary goal of close observation is to determine as quickly as possible whether observed abnormal findings are transient and will resolve spontaneously or will progress to marked serum aminotransferase elevation or evidence of functional impairment, as indicated by rising bilirubin or INR (international normalized ratio), which represent substantial liver injury.

Close observation includes:

- **Repeating liver enzyme (AST, ALT, ALP) and serum bilirubin tests two or three times weekly. If total bilirubin is elevated, obtain direct bilirubin.** Frequency of retesting can decrease to once a week or less if abnormalities stabilize or drug has been discontinued and the subject is asymptomatic.
- **Obtaining additional tests, as appropriate, to evaluate liver function, (e.g. INR); diagnostic measures (e.g. ultrasound of the liver), serum ammonia, etc.**
- Obtaining a more detailed history of symptoms and prior or concurrent diseases. Update the appropriate eCRFs (if applicable).
- Obtaining a history of concomitant drug use (including nonprescription medications and herbal and dietary supplement preparations), alcohol use, recreational drug use, and special diets. Update the appropriate eCRFs (if applicable).
- Ruling out other immediately apparent possible causes of aminotransferase (ALT or AST) elevation and hyperbilirubinemia, as described below.
- Obtaining a history of exposure to environmental chemical agents.
- Considering gastroenterology or hepatology consultations.

Relevant supplemental information must be collected and entered in the appropriate eCRF(s) for instances observed after the implementation of protocol version 7.

Evaluating Data for Alternative Causes

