3.0 Introduction

This statistical analysis plan (SAP), prepared jointly by AbbVie and EORTC, will provide details to elaborate statistical methods for efficacy and safety data in adult subjects collected as outlined in the protocol version 6 for Study M14-483 dated January 18, 2017 and will describe analysis conventions to guide the statistical programming work. For pediatric sub-study, a separate SAP will provide details for statistical methodologies and data conventions.

Efficacy and safety analyses will be performed using SAS Version 9.2 or higher (SAS Institute, Inc., Cary, NC 27513) under the UNIX operating system. The SAP will be signed off before the study database is locked.

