4.6 Type I Error Adjustment Procedures for Multiple Testing

Although Section 8.2.3.6 of the study protocol dated November 25, 2015, describes a different testing order, the multiple testing strategy was revised per diagram (Figure 2) in version 1.0 of the SAP finalized prior to the interim analysis of efficacy data. Given the clinical importance of an overall survival (OS) benefit in recurrent GBM subjects, comparing first OS of combination arm (ABT-414 + TMZ) vs. control and next OS of ABT-414 monotherapy vs. control, followed by comparison of other secondary efficacy endpoints in a similar sequence, is considered a simple and more clinically relevant approach to test the various study hypotheses. At the final analysis, the treatment effects will be tested at the adjusted significance level mentioned in the previous section. The proposed multiple testing strategy based on the above fixed hierarchical sequence preserves the family-wise type-I error at 1-sided 2.5% level. This change was made by consensus agreement among the study sponsors (EORTC and AbbVie Inc.) without any knowledge of unblinded efficacy data from the trial and prior to interim futility analysis.

To describe the multiplicity adjustment procedure fully, consider the following null hypotheses:

H1: Arm 1 is not superior to Arm 3 in OS.

H2: Arm 2 is not superior to Arm 3 in OS.

H1a: Arm 1 is not superior to Arm 3 in PFS.

H2a: Arm 2 is not superior to Arm 3 in PFS.

H1b: Arm 1 is not superior to Arm 3 in ORR.

[figure not shown]
H2b: Arm 2 is not superior to Arm 3 in ORR.

H1c: Arm 1 is not superior to Arm 3 in OS among EGFR vIII mutated subjects.

H2c: Arm 2 is not superior to Arm 3 in OS among EGFR vIII mutated subjects.

To maintain the overall type I error control for the study, these null hypotheses will be tested in a fixed sequence of {H1, H2, H1a, H2a, H1b, H2b, H1c, H2c}. Hypothesis H1 will be tested first, and no further tests will be performed if H1 is not rejected. Thereafter, each hypothesis will be tested in the order specified if and only if H1 and all preceding null hypotheses are rejected. Otherwise testing in the hierarchical sequence will stop.

Figure 2. Testing Procedure

All other endpoints, e.g., PFS in EGFRvIII mutated, global health/QoL status (GHQs), and neurological disease-free survival (NDFS) are considered exploratory and will be tested at a 2-sided 5% level of significance.

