10.3 Efficacy Analyses

Statistical analyses will be performed to compare the primary and secondary endpoints described in Section 10.2 between each treatment arm (Arm 1 or Arm 2) and control (Arm 3) following the fixed sequence described in Section 4.6.

Analysis Methods for TTE Endpoints

For all TTE endpoints, differences between the treatment arms and the control arm will be assessed by a log-rank test stratified by the randomization stratification factors described in Section 4.3. The p-value obtained from the stratified log-rank test will be considered as the primary basis for determination of statistical significance for the TTE endpoints.

Kaplan-Meier (KM) estimates of the survival distribution of each TTE endpoint in Arms 1 – 3 will be estimated and plotted. Two-sided 95% CIs for the KM curves will be computed using Greenwood's formula and plotted. The median for the TTE and the probability of being event-free at 6 months, 1 year (12 months) and 2 years (24 months), and their 95% CIs will be estimated from the KM curve and its 95% CI for each treatment arm.

The hazard ratios of the two treatment arms over the control arm, adjusting for the main effects of randomization stratification factors as covariates, and their 95% CIs will be estimated using a Cox's proportional hazards model (score test).

The above-mentioned methods will be referred to as *primary survival analysis methods* for the remainder of this SAP. Analysis of the following endpoints will be performed using these primary survival analysis methods:

- Overall Survival (OS)
- Progression-Free Survival (PFS) assessed by IRC
- OS and PFS in subjects with EGFRvIII Mutation (in the Ev3M population)
- Neurological Deterioration-Free Survival (NDFS)
- OS and PFS in the subgroup of subjects with timing of relapse (< 16 weeks vs. \geq 16 weeks after the first day of the last TMZ cycle)
- Time to Tumor Response (TTR)
- Duration of Response among treatment responders (CR or PR). The time origin for calculating DOR is not the date of randomization.

Objective Response Rate (ORR)

The number and percentage of subjects with objective response will be presented by treatment arm. The objective response (CR and PR) rate will be reported with exact (binomial) two-sided 95% CI for each treatment arm.

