12.0 Summary of Differences Between EORTC and AbbVie Analyses

EORTC and AbbVie Inc. may follow slightly different approaches for the analyses of certain types of study data. EORTC will perform analyses primarily for the purposes of certain clinical publications. Such analyses, unless also performed by AbbVie (perhaps using different approach), may be included in AbbVie's Clinical Study Report of this study.

While there may be other differences, the following is a summary of differences in EORTC planned analysis from the pre-specified analysis methods described above that AbbVie and EORTC have been able to identify at the time of drafting this SAP (paragraph numbering refers to sections of the present document):

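### Does it matter that SAP 10.3 takes its hazard ratios from a covariate-adjusted Cox model while Protocol 8.2.3 uses a stratified one?

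*SAP*

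**What the plan says.** Protocol 8.2.3.1 tests OS by a log-rank test stratified by the randomization factors and takes the HR from Cox's "proportional hazards model (score test) stratified by randomization stratification factors". Sections 8.2.3.2 (PFS) and 8.2.3.5 (NDFS) do the same. Section 8.2.3.4 extends this to OS and PFS in EGFRvIII-mutated patients: "The same methodology as for analyses in the whole cohort will be applied". Protocol 8.4 counts both the stratified log-rank test and the stratified Cox model as the primary efficacy analysis.

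SAP 10.3 keeps the stratified log-rank test and gives it the deciding role: "The p-value obtained from the stratified log-rank test will be considered as the primary basis for determination of statistical significance". It then estimates the HRs and their 95% intervals from a Cox model "adjusting for the main effects of randomization stratification factors as covariates". That sentence covers every time-to-event endpoint in the section, including time to tumor response and duration of response.

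**The concern.** These are two different models. One has a separate baseline hazard in each stratum. The other has a single baseline hazard and additive factor effects on the log-hazard scale. Each document treats its own model as part of the primary methods, so the pre-specified HR and interval for OS look ambiguous.

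The score test of the protocol's model is the stratified log-rank test (apart from ties), so its interval nearly always agrees with the deciding test. The SAP's model has no such link. A borderline trial could report an interval that excludes 1 beside a non-significant test. In a fixed sequence that stops at the first failure, that could put a favourable-looking interval next to a failed OS hypothesis.

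**Working it through.** **1. The plan's own figure.** SAP 4.4 gives 118 deaths per comparison, HR 0.54, one-sided 2.5% and power 91.7%. Schoenfeld's formula gives z = (√118 / 2) × |ln 0.54| − 1.960 = 5.431 × 0.6162 − 1.960 = 1.387, so power = Φ(1.387) = 0.917. This reproduces the stated figure, and no Cox model enters it. The critical HR is exp(−1.96 × 2/√118) = 0.697.

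**2. Where an HR could decide something.**
- Final efficacy: the stratified log-rank test, in both documents.
- Re-randomization test (SAP 10.4): uses log-rank p-values.
- Interim futility: this rule does use an HR (PFS, cut-off 0.91). SAP 4.5 ties it to the protocol's statistical section and records that the IDMC received the report in September 2016. SAP 10.3 does not alter it.

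**3. Size of the strata.** Region (3) × performance status (2) × timing of relapse (2) = 12 strata, so 118 / 12 ≈ 9.8 deaths per stratum in each comparison.

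**4. Simulation.** Two separate programs compared Wald 95% intervals with the one-sided 0.025 stratified log-rank test at 118 deaths.
- *Simulation 1*: 240 patients 1:1:1, the protocol's accrual, exponential survival with control median 7 months. It used either minimization or balanced allocation within cells: 4 factor scenarios × 3 HRs × 2 allocations × 4,000 = 96,000 trials. Assumed factor HRs ranged from none to 2.0, with one interaction scenario.
- *Simulation 2*: 160 patients in two arms with approximate minimization, 9 scenarios × 4,000 = 36,000 trials. Three scenarios had non-proportional hazards between strata.

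The 60% share of early relapse follows Protocol 1.2. The other strata shares and all factor effects are assumptions.

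| True HR | Covariate interval v test, sim 1 | sim 2 | Stratified interval v test, both |
|---|---|---|---|
| 0.54 | 4.2-6.5% | 5.9-7.1% | at most 0.4% |
| 0.70 | 9.6-12.7% | 11.2-13.1% | at most 0.7% |
| 1.0 | 1.4-2.4% | 1.3-1.6% | at most 0.1% |

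HR 0.70 lies almost on the critical value of 0.697, so that row is near the worst case.

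*Direction (simulation 1).* At HR 0.54 the interval alone excludes 1 in 3.4-5.4% of trials, and the test alone rejects in 0.8-1.2%. At HR 1.0 the two are about even (0.8-1.2% v 0.6-1.2%).

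*Validity for OS.* Coverage of the covariate interval is 93.8-95.4% (simulation 1) and 94.0-95.4% (simulation 2). For the stratified interval it is 94.5-95.8% and 94.5-95.5%.

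*Estimates.* At true HR 0.54 the geometric-mean HR is 0.535-0.540 stratified v 0.529-0.536 covariate. The largest gap between medians in simulation 2 is 0.541 v 0.552, under non-proportional hazards.

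**5. Price of the stratified model.** The mean standard error of the log HR for OS is about 0.20 stratified v 0.19 covariate. If half the patients carry EGFRvIII (Protocol 1.3), that subset has about 118 × 0.5 = 59 deaths. At HR 0.54 its standard error is then 0.302-0.313 v 0.276-0.279, which is 18-27% more variance with stratification. Disagreement with the test there is 14.6-17.2% v 0.7-1.3%. These two OS hypotheses come seventh and eighth in the fixed sequence.

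**6. Duration of response.** The same SAP sentence governs this endpoint, for which Protocol 8.2.3.3 asks only for Kaplan-Meier medians. A small check (400 trials per setting, HR 0.54, assumed responder numbers) gave a median standard error of 0.51 stratified v 0.43 at 40 responders, and 1.14 v 0.87 at 16. At 16 responders, 19% of stratified fits were unusable, against 6.5%.

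**The case for a change.** The best case for a change is procedural. SAP 4.6 explains another departure openly ("Although Section 8.2.3.6 of the study protocol dated November 25, 2015, describes a different testing order"), and the supplied protocol now has the SAP's testing order. The Cox model was neither reconciled nor explained. Most disagreements at HR 0.54 and 0.70 in simulation 1 (69-86%) also favour the experimental arm, and aligning the models would cost one sentence.

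It stands that the documents differ and that nothing in them shows whether this was deliberate. The rest is weaker:

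- SAP 12.0 introduces its list with "the following is a summary of differences in EORTC planned analysis from the pre-specified analysis methods described above". It compares the two organizations, not the SAP with the protocol, so its silence says little. SAP 14.0 records changes to the SAP itself.
- The SAP was written to data collection "as outlined in the protocol version 6 for Study M14-483 dated January 18, 2017". The supplied protocol is later, since Appendix L refers to liver data "for instances observed after the implementation of protocol version 7". The version that the SAP authors worked from is not available for comparison.
- At HR 0.54, an interval that excludes 1 beside a non-significant test is the more precise model detecting a true effect. Agreement would be gained mainly by widening the interval.
- A note that the interval does not decide significance would largely repeat what SAP 10.3 says about the log-rank p-value.

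**Conclusion.** No change follows. The SAP is the detailed analysis document. An analyst who follows it exactly makes the same efficacy decision as under the protocol and reports an HR with about nominal coverage and slightly better precision. The report need only say which Cox model its HR comes from, as is ordinary practice. Choosing between agreement with the log-rank test and a tighter estimate over 12 sparse strata is a fair trade-off, and either choice is defensible.

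The remaining cost is that interval and test disagree in about 4-7% of trials at the design HR, with a peak of about 10-13% near HR 0.70. These rates rest on assumed factor effects and strata shares. PFS and NDFS were not simulated. The EGFRvIII figures also assume that a random half of patients is mutated. That the test, alpha and power do not depend on the Cox model rests on none of these assumptions.

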8.2.3.3 Radiological response

In the ITT (RANO criteria assessed by IRC):

The best overall response will be presented in contingency table with frequencies and percentages. The objective response (ORR: CR/PR) and complete response rates will be reported with exact (binomial) two-sided 95% CI. The medians of objective (PR/CR) and complete (CR) response duration will be estimated from the Kaplan-Meier curves. The Reflected Method will provide two-sided 95% CI.

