The duration of overall response (DOR) will be analyzed only for the subset of subjects who experience a complete or partial response (CR or PR). For a given subject, DOR will be defined as the number of months from the day the criteria are met for CR or PR by IRC (whichever is recorded first) to the date of progressive disease or death, whichever comes first. If a subject is still responding (i.e., has not progressed nor died after CR or PR), then the subject's data will be censored at date of the last radiological assessment.

Time to Tumor Response (TTR)

Time to tumor response is defined as the time from the date of randomization to the observation of objective response (CR or PR).

For a subject who neither respond nor progress, TTR will be censored at the subject's last tumor assessment date. For subjects who progress and never respond, TTR will be set by convention as the longest time from randomization to the last tumor assessment observed across all subjects; i.e., $\max(\text{last tumor assessment date} - \text{randomization date} + 1)$ for all subjects. The distinction in censoring rule is made here since, at the time of censoring, the

former set of subjects would still have a possibility of experiencing a response (the event of interest), while the latter set of subjects never will.

Best Overall Response Rate (BRR)

Best overall response is the best response assessed by IRC from the date of randomization until disease progression or death, whichever comes first. Subjects who did not have post-baseline assessments will be considered "not-assessed." Subjects who had only one response that required a confirmatory MRI scan, which was not performed, will also be considered not-assessed.

Objective Response Rate (ORR)

Objective response includes best overall responses – complete response (CR) and partial response (PR) – assessed by IRC per RANO criteria from the date of randomization until disease progression or death, whichever comes first. All objective responses (CR and PR) must be confirmed by repeat MRI 4 weeks later than the first time when CR or PR is identified. Any subject who did not meet CR or PR including those who did not have post-baseline radiological assessments will be considered as non-responder.

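### SAP 10.3 puts a between-arm log-rank p-value and hazard ratio on duration of response among responders only, a non-randomised comparison that can point against the arm with more responders

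*SAP*

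**What the plan says.** SAP 10.2 restricts the population: "The duration of overall response (DOR) will be analyzed only for the subset of subjects who experience a complete or partial response". The clock starts at first CR or PR.

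SAP 10.3 then sets the method. "For all TTE endpoints, differences between the treatment arms and the control arm will be assessed by a log-rank test stratified by the randomization" factors, and "The p-value obtained from the stratified log-rank test will be considered as the primary basis for determination of statistical significance for the TTE endpoints". The effect measure is described as "The hazard ratios of the two treatment arms over the control arm, adjusting for the main effects of randomization stratification factors as covariates", from a Cox model with 95% CIs. The SAP labels this package its primary survival methods and lists the endpoints that receive it; the last entry is "Duration of Response among treatment responders (CR or PR". The only caveat there is that the time origin is not randomization. SAP section 12 removes time to tumor response from the EORTC analysis but leaves duration of response in.

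The protocol is more modest. Section 8.2.1.2.2 has duration of response, an exploratory endpoint, computed in each arm. Section 8.2.3.3 says: "The medians of objective (PR/CR) and complete (CR) response duration will be estimated from the Kaplan-Meier curves", with two-sided 95% CIs. It mentions no test and no hazard ratio for duration.

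SAP 10.3 also opens by confining its between-arm comparisons to primary and secondary endpoints in the fixed sequence, which does not fit with an exploratory endpoint appearing on the list that follows.

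**The concern.** Response happens after randomization, and it is itself a treatment outcome that the trial tests (H1b and H2b). If ABT-414 changes who responds, the responders in its arm and in the control arm are different kinds of patients. A log-rank test or hazard ratio between them mixes any drug effect on duration with this selection. Three baseline stratification factors do not remove it.

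The awkward case is an active drug. If it turns less sensitive tumours into responders and those responses are shorter, its typical duration falls below control although no patient has lost anything. The report would then carry a p-value and hazard ratio that appear to count against the arm with the better response rate. Responders are also likely to be few, and the log-rank test splits them over 12 cells.

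**Working it through.** **The plan's own figures.** Neither document gives a figure for duration of response. The nearest is the OS power, which checks the formula used below: power = Φ(√(d·a(1−a))·|ln HR| − z). With d = 118, a = 1/2, HR 0.54 and z = 1.960: √29.5 × 0.616 − 1.960 = 1.387, and Φ(1.387) = 91.7%, as stated in SAP 4.4. The present point does not depend on it.

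**Inputs from the documents.** 240 patients randomized 1:1:1, so 80 per arm (Protocol 8.1.1, SAP 4.2). Strata: region (3) × performance status (2) × timing of relapse (2) = 12 cells (SAP 4.3).

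**Assumed.** Response rates, control v ABT-414: 5 v 15%, 10 v 20%, 15 v 30%. Multiplied by 80, these give 4 v 12, 8 v 16 and 12 v 24 responders. Cell shares: region 30/55/15, performance status 35/65, timing 60/40 (the last matches the historical split in Protocol 1.2).

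**Step 1: selection with no drug effect on duration.** Let sensitivity X ~ N(0,1). A patient responds if X exceeds the arm's threshold t, the upper response-rate quantile. Log duration = βX + noise (SD 0.5), identical in both arms. The median m among responders solves P(βX + noise ≤ ln m | X > t) = 1/2. Ratio of medians, ABT-414 to control:

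| β | 5 v 15% | 10 v 20% | 15 v 30% |
|---|---|---|---|
| 0 | 1.00 | 1.00 | 1.00 |
| 0.25 | 0.880 | 0.915 | 0.905 |
| 0.5 | 0.774 | 0.836 | 0.818 |
| 1 | 0.595 | 0.695 | 0.665 |

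Hand check: mean X among responders is φ(t)/rate, which is 2.06 at 5% and 1.55 at 15%. So the ratio is roughly exp(β × (1.55 − 2.06)): 0.88, 0.77 and 0.60 for β = 0.25, 0.5 and 1.

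**Step 2: a different model.** Suppose 10% respond in either arm (median 6 months, no drug effect) and a further 10% respond only on ABT-414 (median 3 months), with exponential durations. Mean time in response over all randomized patients is 0.10 × 6/ln 2 = 0.87 months on control and 0.87 + 0.10 × 3/ln 2 = 1.30 months on ABT-414, so ABT-414 is better. The responder-only hazard ratio is 1.32; in 4,000 simulated trials it exceeded 1 in 72% and was significantly against ABT-414 in 9% (unstratified log-rank, no censoring). With a true hazard ratio of 0.8 among the shared responders, and 10 to 20% extra responders at a median of 2 to 3 months, the responder-only value is 1.14 to 1.51. With 0.54, and extra responders at a median of 3 months, it is 0.90 to 1.10.

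**Step 3: sparse cells.** For cell share p, the expected number of empty cells is Σ(1−p)^(nc+nt), and of one-arm cells Σ[(1−p)^nc + (1−p)^nt − 2(1−p)^(nc+nt)]. Neither kind adds anything to a stratified log-rank statistic. The last two columns come from 3,000 simulated replicates.

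| Responders | Empty | One arm only | Both arms | Log-rank variance, 12 cells v none | Kept |
|---|---|---|---|---|---|
| 4 v 12 | 4.0 | 5.7 | 2.3 | 0.91 v 2.35 | 39% |
| 8 v 16 | 2.7 | 5.2 | 4.2 | 2.13 v 4.51 | 47% |
| 12 v 24 | 1.6 | 4.5 | 5.9 | 3.92 v 7.18 | 55% |

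With responder counts held fixed at these values, the shares kept are 38%, 46% and 54%.

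**Step 4: power before that loss.** For HR 0.54 at two-sided 5%, with every responder having an event: 16 responders give Φ(√(16 × 0.75 × 0.25) × 0.616 − 1.96) = 19%; 24 give 30%; 36 give 41%.

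**The case against.** Four arguments for the plan deserve weight.

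- *The protocol does not forbid a test.* A reader might infer that Protocol 8.2.3.3 restricts duration of response to medians. It does not say so. The same section gives no test for ORR, which is in the confirmatory sequence, and Protocol 8.2.3.6 has all other endpoints tested at two-sided 5%, a rule that can be read to cover this one. The SAP may fairly be called an elaboration. This stands, but permission to test does not make a responder-only comparison interpretable.
- *Nothing decisive rests on it.* The endpoint is exploratory and outside the H1 to H2c sequence, and the SAP states the responder restriction openly. This stands too. A reading that type I error, power, arm dropping or the OS conclusion is at risk has no support in the documents.
- *The size of the bias is assumed.* The plan gives no adult response rates and no link between sensitivity and duration. With no link the ratio is 1.00, and a real benefit on duration can offset the selection, as the 0.90 to 1.10 range shows. This limits what can be said about size. It does not restore comparability.
- *The sparse-cell argument has limits.* A reader might infer that most of the 12 cells hold one arm only, or that the hazard ratio suffers the same loss. Under the assumed shares only about 4.5 to 5.7 cells hold one arm only; it is empty and one-arm cells together that reach about 6 to 10. The Cox model uses the factors as covariates, so the 12-cell loss does not carry over to it in that form.

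A label calling the comparison descriptive would help, but would leave in the report a p-value and hazard ratio with no clear treatment-effect meaning.

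**Conclusion.** The concern holds as an interpretation problem. SAP 10.3 prescribes a between-arm p-value and hazard ratio for a group formed after randomization on an outcome that treatment may change, and this goes beyond the per-arm summary that the protocol describes. With no drug effect on duration, the median ratio ranges from 1.00 (no link between sensitivity and duration) through 0.88 to 0.92 (weak link) to about 0.60 to 0.84 (moderate to strong link), under the assumed response rates. The stratified log-rank test would keep about 38 to 55% of the unstratified information, given those rates and the assumed cell shares. The possible harm is a misleading exploratory result in the report, not a wrong trial conclusion. The change is worth making because it costs almost nothing.

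**What to change.** Delete duration of response from the list in SAP 10.3 and state: *DOR is summarised per arm with the Kaplan-Meier median and 95% CI; no between-arm test or hazard ratio.* This agrees with Protocol 8.2.3.3 and removes the mismatch with the opening sentence of SAP 10.3. The same statement should cover the investigator-assessed version in SAP 10.5.

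Cost: one exploratory p-value and hazard ratio per comparison are no longer reported. The per-arm curves, medians and intervals stay. The sample size, the 118 deaths per comparison, the 91.7% power and the testing sequence do not change.
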